## 1.0 Objectives\*

- 1.1 The purpose of this study is to investigate the effects that a volitional maximal cardiovascular exertion test (the Bruce Treadmill Protocol) has on performance of the Forward-Step-Down (FSD) test, and to investigate how performance on the FSD test changes at multiple time points following the fatigue test.
- 1.2 Our hypotheses for this study are as follows:
  - Null ( $H_0$ ): Participants will not demonstrate a change in score on the FSD test after performance of the Bruce test at any time point.
  - Alternate ( $H_1$ ): Participants will demonstrate a change in score on the FSD test after performance of the Bruce test at one or multiple of the repeated measurements.

## 2.0 Background\*

- 2.1 The FSD test has been shown to correlate with movement quality. Deficits in strength and flexibility that result in movement impairments are associated with scores on the test delineating “moderate” movement quality. Fatigue may play a role in increased injury risk, with fatigued participants in numerous studies showing compromised movement patterns that increase risk of injury. At this time, many of the screening tools used to determine the impact of fatigue on a player’s ability to continue to play/practice involved dynamic or explosive movements, and rely on indicators such as femoral internal rotation or hip adduction angles at initial contact to grade movement patterns. These biomechanical indicators may be difficult for non-professional personnel to observe, limiting their use outside a clinic. There is currently no research on the role of the FSD test in assessing for changes in movement pattern that result from fatigue.
- 2.2 N/A
- 2.3 The literature currently acknowledges that fatigue results in altered movement patterns. Several studies have investigated the impact that fatigue has on performing challenging movements, such as plyometric drop jumps, cutting, jumping and running, and landing. However, with higher level assessments such as these, there is an increased risk for injury if performed while fatigued. Therefore, a lower level test, such as the FSD test, would be ideal as a safe and effective screening tool to look at the impact of fatigue stimulus (game play) on a person’s movement quality. As stated above, the FSD test has been validated as a measure of movement quality, with acceptable interrater reliability. In addition, poor movement quality during the FSD test has been shown to correlate with several impairments such as hip abductor strength and poor flexibility. Existing literature discusses the impact of the hip abductors on knee position and risk for knee injury. Therefore, a functional test that assesses not only movement quality but

PROTOCOL TITLE: The Effect of Cardiovascular Fatigue on Performance of the Forward-Step-Down Test

identifies possible causes of poor movement would be ideal for preventing injury. Research has shown difference in postural balance following aerobic fatigue depending on the time since fatigue, with poor performance immediately following but improved performance 10 minutes after the fatigue stimulus was stopped. Therefore, this study will examine the FSD test at one, five, and ten minutes following the cardiovascular fatigue protocol in order to discern performance differences in movement quality related to time/recovery. These differences may be important because if the FSD test can be used as a screening tool to examine a person's fatigue level, it is important to also know the appropriate time to use the test in order to get accurate results.

In this study, the Bruce test is used to achieve cardiovascular fatigue. Clinically it is a "VO2max" (maximum volume of oxygen consumption) prediction test and is intended to continue to the point of failure (maximum test). In a true VO2max test, the participant performs the cardiovascular test until respiratory spirometry measures a plateau of the VO2, or oxygen consumption, between two workloads. This is indicative of that participant's maximum cardiovascular physiological limits. During a true VO2max test, respiratory gases are analyzed as well as heartrate, blood pressure, and sometimes blood lactate samples are obtained. Together these values determine the success in reaching a true VO2max test, demonstrate cardiovascular fatigue, and ensure safety of the participant. Often, this point is not reached in untrained or unhealthy individuals.

Performing a true VO2max test is more expensive and time-consuming for the participant than performing a maximal or submaximal graded exercise test. Therefore, the Bruce protocol uses mathematical derivation to predict VO2max from the participant's performance on the Bruce. To estimate an accurate prediction of the VO2max and ensure cardiovascular fatigue, the target heart rate is often set at  $\pm 10$ bpm of the age-predicted maximum heart rate when using a lower error formula such as the Tanaka formula. Therefore, in this study participants' age-predicted maximum heart rate will be calculated using the formula derived by Tanaka with an acceptable variability of  $\pm 10$ bpm at the maximum heart rate measured during the Bruce. The Tanaka formula is accurate for a population of healthy men and women. In this study, "healthy" is defined as being in the "low risk" category for exercise as stated by the American College of Sports Medicine, and is one of the inclusion criteria for this study.

### 3.0 Inclusion and Exclusion Criteria\*

- 3.1 Participants will be recruited from current physical therapy students in the class of 2020 who are enrolled in PHTH 7565. During the consent process, the participants will be screened using the American College of Sports Medicine's guidelines for safe participation in vigorous exercise. By meeting the ACSM criteria, the participant is considered low risk for adverse events while participating in vigorous activity. Finally, in order for

PROTOCOL TITLE: The Effect of Cardiovascular Fatigue on Performance of the Forward-Step-Down Test

the student to participate, they must achieve  $\pm 10$ bpm of their predicted maximum heartrate, as calculated by the Tanaka formula as stated above.

- 3.2 Exclusion criteria are pre-existing cardiovascular conditions or diseases that prevent participation in a maximal effort test without physician clearance per the ACSM guidelines. Participants who do not reach their calculated target heart rate by the end of the Bruce protocol will be withdrawn from the study and will not complete post-fatigue testing.
- 3.3 The investigators plan to include the special population of students in this study. To mitigate potential risk of coercion, participation in the study will be voluntary. While the Bruce protocol testing is part of one of the mandatory laboratory activities for the exercise physiology class (PHTH 7565), participation in the study is not mandatory and it will be explained that participation in the study will not impact the students' grades in any class in any way. The testing will be performed as an adjunct to exercise testing performed in the regularly scheduled exercise physiology class, and the researchers are not responsible for grading in the exercise physiology class.

**4.0 Study-Wide Number of Subjects\***

N/A

**5.0 Study-Wide Recruitment Methods\***

N/A

**6.0 Multi-Site Research\***

N/A

**7.0 Study Timelines\***

7.1 Describe:

- Prior to performing the testing, participants will be consented and screened for inclusion and exclusion criteria at the end of an exercise physiology class during the summer 2018 semester. This will occur before the students begin their exercise testing labs in which the Bruce protocol is performed. Following consenting, participants will proceed to the testing during the four-week data collection period during the summer 2018 semester.
- Each participant will perform the pre-and post-testing in the same day. The pre-fatigue FSD test occurs just prior to the fatigue (Bruce) protocol, and the post-testing will occur at one, five, and ten minutes after completion of the fatigue protocol. Initial resting heart rate will be measured, as will heart rate at 0, 30, and 60 seconds following completion of the Bruce to ensure appropriate heart rate responses to exercise for a healthy young adult as per the inclusion criteria of

PROTOCOL TITLE: The Effect of Cardiovascular Fatigue on Performance of the Forward-Step-Down Test

participants being “low risk” for adverse events during vigorous exercise.

- The expected duration to obtain all necessary participants is up to 4 weeks.
- The estimated time for the researches to perform the primary analysis is 3 months
- The estimated time to prepare the manuscript for publication is 1 year.

## **8.0 Study Endpoints\***

- 8.1 The primary endpoint will be collection of the FSD test scores and maximum heartrate on the Bruce protocol. The secondary endpoint will be submission for publication.
- 8.2 During the fatigue (Bruce) protocol, the student will be monitored each minute for heartrate and rating of perceived exertion (RPE). Should either exceed safe values, or should the participant demonstrate adverse heart rate reaction to the exercise as stated in the ACSM termination criteria, the test will be terminated. The participant also has control over the treadmill and can halt testing at any time should adverse events occur, or should the participant wish to stop the protocol. FSD testing will be halted if adverse events or injury occurs prior to or during the testing process. RPE has been established as a subjective correlation to physiological fatigue, and is accepted as a non-invasive measure of physiological fatigue that will be used as a reinforcement of heartrate monitoring. There are no secondary safety end points.

## **9.0 Procedures Involved\***

- 9.1 This study will be a repeated-measures design, with all participants undergoing both pre- and post-fatigue FSD test assessments. Two orthopaedic specialist physical therapists will perform the FSD assessments. The investigators will review scoring guidelines per the Park article, and will practice scoring the test prior to data collection to ensure good interrater reliability. Scores on the FSD test from each assessor will be averaged after data collection and prior to data analysis, with each assessor blinded to the other’s score prior to averaging the scores. Participants will be healthy physical therapy students. Fatigue will be induced via the Bruce protocol used in assessment of maximum cardiovascular capacity. The treadmill used is an HP Cosmos Quasar (HP Cosmos, Germany). The heart rate monitors used are Polar monitors (Polar Electro Inc, Bethpage, NY)
- 9.2 The FSD test grades the participant on movement quality during a repeated step down from a 20 cm step. The weight bearing leg will be the dominant leg (the leg the participant would use to kick a ball) as used in the Park et al experiment. The FSD test consists of five repeated movements of the forward step down, with one score given for the whole set of five repetitions. For each set of five movements, the rater observes and produces

**PROTOCOL TITLE: The Effect of Cardiovascular Fatigue on Performance of the Forward-Step-Down Test**

one score for that set of five movements. For data analysis, the investigators will use the average of each score for each FSD test. For example, on the pre-test for a participant, if one investigator scored the pre-test FSD a 2/6, and the second investigator scored the pre-test a 1/6, the “averaged” score for the participant’s pre-test is a 1.5/6. This same procedure would be repeated for the three post-test FSD tests.

The Bruce protocol is self-limited with participants stopping at maximal exertion. Maximal exertion will be defined as  $\pm 10$ bpm of the participants predicted maximum heartrate as calculated by the formula “ $208 - (0.7 \times \text{age})$ ” derived by Tanaka from a population of healthy men and women. The  $\pm 10$ bpm heart rate cutoff has been used as a benchmark of achieving maximal exertion in a maximal exercise test based off the calculated maximum heart rate using the Tanaka formula. The participants’ Borg Rating of Perceived Exertion (RPE) will also be recorded as part of the Bruce protocol; however, since the participants know they will have to perform the FSD test following the Bruce protocol, the investigators will use heartrate instead of RPE as a metric for exertion due to its more objective nature and to avoid a possible threat to validity of the fatigue protocol. During the Bruce protocol, treadmill speed and incline are increased every three minutes until the subject volitionally stops the test at maximal exertion. Heartrate and RPE are monitored each minute during the Bruce protocol, with assessment of blood pressure prior and following the treadmill test as part of the Exercise Physiology class.

9.3 Table of events and tests to occur:

Events/Procedure	Frequency
Informed Consent	1
FSD test	4
Bruce test	1
Notification of results	1

9.4 Describe:

- Participants will be screened for health contraindications to performing the testing by use of the ACSM’s screen for participation in vigorous activity (see flow chart on Informed Consent document). No other data will be collected from the participant’s health record. They will be informed of their right to stop testing and withdraw from the study at any point. Heart rate will be monitored each minute during the maximal testing to ensure appropriate responses occur; testing will be

PROTOCOL TITLE: The Effect of Cardiovascular Fatigue on Performance of the Forward-Step-Down Test

halted by the investigators if heartrate fails to respond appropriately, the patient shows signs of hypoxia, or other injury/adverse events occur.

- N/A
- No source records will be required for the purposes of this study

9.5 The study will collect pre- and post-fatigue FSD test scores. Heartrate will be monitored and the maximum heart rate during the Bruce will be recorded to ensure the participant meets the  $\pm 10$ bpm cutoff, but will not be stored for further use.

9.6 N/A

## 10.0 Data and Specimen Banking\*

N/A

## 11.0 Data Management\* and Confidentiality

11.1 Since this study involves multiple repeated-measures over time, dealing with an ordinal level dependent variable, a Friedman's ANOVA would typically be used for data analysis. However, at least one previous study has analyzed this measure via parametric statistics, so we could potentially also pursue a Repeated Measures ANOVA if our data meets all parametric assumptions. Since our alternate hypothesis is two-tailed, our p-value will be divided by two for accurate significance assessment

11.2 To the investigators' knowledge, there is no previous literature examining the effects of an activity/intervention on a within-subjects change in performance on the FSD test. As a result, no within-subjects effects sizes were available for an a priori power-analysis for required sample size. In previous work examining the inter-rater reliability of the FSD test, Park, et al. used an effect size of 1.26, based upon the work of Rabin and Kozol, in which they measured the amount of ankle dorsiflexion and compared groups scoring differently on the FSD test in this anthropometric measure. We therefore, used 0.5 as our effect size because the current study design differs from the Rabin and Kozol study design, and given their large effect size the investigators felt justified in setting a moderate effect size for the power analysis. The power analysis used an alpha of .05 and power of .80 for a two-tailed hypothesis via a repeated measures, within factors ANOVA analysis. This power analysis determined the need for nine participants. With 37 students in the class, we have more potential participants than needed to ensure the required power to observe a statistical result if it exists.

11.3 The Excel sheet will be kept in in a password protected file on password locked computers in the PI and co-investigator's offices. Consent forms will be secured in a locked file cabinet in the PI's office.

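### Section 11.1 halves the p-value of an omnibus test because the hypothesis is two-tailed; followed as written, this tests at 10% instead of 5%

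*Protocol*

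**What the plan says.** - **Hypothesis (section 1.2).** The alternative has no direction: "Participants will demonstrate a change in score on the FSD test after performance of the Bruce test at one or multiple of the repeated measurements".
- **Design (sections 7.1 and 9.2).** Each participant has one pre-test and three post-tests, at one, five and ten minutes, so there are four repeated scores.
- **Analysis (section 11.1).** The default is rank-based: "a Friedman's ANOVA would typically be used for data analysis". A parametric route is left open: "we could potentially also pursue a Repeated Measures ANOVA if our data meets all parametric assumptions".
- **Decision rule (section 11.1).** "Since our alternate hypothesis is two-tailed, our p-value will be divided by two for accurate significance assessment".
- **Significance level (section 11.2).** "The power analysis used an alpha of .05 and power of .80 for a two-tailed hypothesis via a repeated measures, within factors ANOVA analysis". No other level appears in the protocol, and nothing elsewhere offsets the halving.

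**The concern.** Dividing a p-value by two is a recognised step in one situation only: a single contrast, a two-sided p-value, and a direction fixed in advance. It gives the one-sided p-value. The protocol applies it to tests that have no direction, and gives as its reason that the hypothesis is two-tailed. That reason argues for leaving the p-value alone.

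The rule governs the only kind of hypothesis test that the protocol describes. If it is followed, a result with p between .05 and .10 is reported as significant at .05, and a claim that exertion changes step-down performance carries about twice the false-positive risk that a reader of section 11.2 would assume.

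**Working it through.** **Inputs.** Four measurements (sections 7.1 and 9.2); alpha .05, power .80, effect size 0.5, nine participants, 37 students available (section 11.2); p-value halved (section 11.1). Assumptions, because the protocol does not give them: the effect size is Cohen's f, and the correlation between measurements (rho) and the sphericity factor (epsilon) take the values shown.

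**1. The stated sample size.** For a within-factor ANOVA with m measurements and N participants, lambda = f² × N × m / (1 − rho), with m − 1 and (N − 1)(m − 1) degrees of freedom when epsilon is 1.

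- m = 4, rho = .5, N = 9: lambda = 0.25 × 9 × 4 / 0.5 = 18, power .922. The smallest N that reaches .80 is 7 (power .813).
- m = 4, rho = .3, N = 9: lambda = 9 / 0.7 = 12.86, power .80, so nine is exactly the requirement.
- Nine is also the requirement at alpha .05 with rho = .5 and epsilon = .75 (power .847), and at alpha .025 with rho = .5 and epsilon = 1 (power .860).

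Nine is therefore consistent with the stated alpha of .05. It does not by itself show which alpha was used.

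**2. Whether the tests have tails to split.** With one contrast, F equals t², so the upper tail of F contains both tails of t. With four measurements, F and the Friedman chi-square are sums of squared deviations and increase with change in any direction. The upper-tail p-value is already the p-value for the alternative in section 1.2.

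**3. What the rule does.** p/2 < .05 is the same as p < .10. At N = 9 the ANOVA degrees of freedom are 3 and (9 − 1) × 3 = 24.

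| Test | Critical value, p < .05 | Critical value, p/2 < .05 |
|---|---|---|
| ANOVA, F(3, 24) | 3.01 | 2.33 |
| Friedman, chi-square(3) | 7.81 | 6.25 |

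**4. Simulated false-positive rates.** There were 40,000 null data sets per sample size. The Monte Carlo standard error is √(.10 × .90 / 40,000) = 0.15 percentage points at 10%. The half-point scores imitate the two-rater average: rounded to 0.5, limited to 0–6, with an assumed mean of 2.5, between-person SD 1.0 and within-person SD 0.8.

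| Test | N | p < .05 | p/2 < .05 |
|---|---|---|---|
| ANOVA | 9 | 4.96% | 9.92% |
| ANOVA | 37 | 4.97% | 10.0% |
| Friedman, no ties | 9 | 4.0% | 9.1% |
| Friedman, no ties | 37 | 4.8% | 9.8% |
| Friedman, half-point scores | 9 | 4.3% | 9.4% |
| Friedman, half-point scores | 37 | 5.0% | 10.1% |

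**5. The other reading: alpha halved to .025.** At N = 9 the simulated error is 2.5% for the ANOVA and 1.9% for Friedman. ANOVA power at N = 9, with f = 0.5, m = 4 and epsilon = 1:

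| rho | Power at .05 | Power at .025 |
|---|---|---|
| 0 | .63 | .51 |
| .3 | .80 | .70 |
| .5 | .92 | .86 |
| .7 | .99 | .98 |

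**The case against.** The strongest reply is that the authors meant to split alpha between two tails and wrote p-value loosely. Their reason, a two-tailed hypothesis, fits that habit, and nine participants is what alpha .025 gives at rho = .5. The error rate would then be about 2.5%, not 10%. To such an author, .05 overall and .025 per tail would not look like a contradiction of section 11.2.

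This stands as a possible account of intent. It does not save the sentence. The text says that the p-value is divided, and an analyst who follows it will divide the p-value. Nine participants also results at alpha .05 under other unstated inputs. An F or chi-square test has no second tail in which to reserve the other half of alpha, so the rule is wrong on this reading too and costs power.

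Two smaller points also stand. The .05 level appears only as a power-analysis input, so its use as the decision threshold is an inference, though no other level is offered. And the power figures depend on inputs that the protocol does not give; the type I error result needs none of them.

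**Conclusion.** The concern holds. The halving rule is invalid for both tests that section 11.1 names, whatever was intended. Taken literally with alpha .05, it sets the nominal type I error at 10%: 9.9–10.0% for the ANOVA and 9.1–10.1% for Friedman in the settings tabulated. Friedman falls a little short of 10% at nine participants because its chi-square approximation is conservative there. The doubling rests only on the literal wording and on .05 as the threshold. If a threshold of .025 was meant, the error is about 2.5% and power is lost, by an amount that depends on the unstated correlation. The two readings differ fourfold in error rate (10% / 2.5%), so the sentence must be corrected before any result is judged.

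**What to change.** Delete the sentence in section 11.1 and put in its place: *The omnibus p-value (Friedman chi-square, or F if the repeated-measures ANOVA is used) is compared, without halving, with alpha = .05.* If pairwise follow-up tests are planned, add that their p-values are two-sided and name the multiplicity rule; the correction does not depend on this addition.

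The cost is one sentence. Data collection is unaffected, and the sample size in section 11.2 was stated at .05, so this change does not disturb it. The only loss is that results with p between .05 and .10 can no longer be called significant. If the authors do want a stricter level of .025, they should state it as alpha in both 11.1 and 11.2 and redo the power calculation at that level.

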## 20.0 Resources Available

20.1 Both investigators have completed orthopaedic residencies and hold current licenses to practice physical therapy in the state of Louisiana. The co-investigator is an Orthopaedic Clinical Specialist, and the PI has recently taken the Orthopaedic Clinical Specialist exam and is awaiting results. PT licensure includes indications and contraindications for maximal exercise testing and prescription for various healthy and unhealthy populations. In addition, the PI has experience working with exercise testing at the Pennington Biomedical Research Center in Baton Rouge, LA. The co-investigator is currently completing his PhD work in Physical Therapy.

20.2 Describe other resources available to conduct the research: For example, as appropriate:

- The class of 2020 that will be enrolled in Exercise Physiology has a total of 37 students. With nine participants needed per the power analysis, there should be no difficulty recruiting the necessary number of participants.
- Both investigators are instructors in the School of Allied Health Professions in the Department of Physical Therapy, and have 30% of their time set aside for research purposes. This time will include recruitment and consenting of participants, testing, data analysis, and writing results for publication.
- The Faculty Practice Clinic in the School of Allied Health Professions is a functioning outpatient physical and occupational therapy clinic. It includes treadmills for aerobic testing, and the appropriate equipment to perform the FSD test. It also includes the emergency equipment necessary to be a functional clinic within regulation.
- The School of Allied Health Professions is part of the larger Health Sciences Center campus. Emergency transportation is available to the hospital, which is adjacent to the Medical School portion of campus. In addition, students have mental health services available for free through the School should this be necessary if a participant has an adverse psychological event to the testing procedures.
- All participants will give voluntary informed consent, by which they will be educated on what tests they will be expected to perform. Both investigators will be able to consent participants into the study. Both investigators will review the protocol prior to the testing sessions, and will keep independent records of FSD test. Prior to each testing sessions, the investigators will clarify any questions regarding

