22.5 N/A

### **23.0 Local Number of Subjects**

23.1 One hundred percent of the subjects will be recruited locally. As stated in the inclusion/exclusion criteria, participants will be included for post-testing only if they achieve  $\pm 10$ bpm of their predicted maximum heartrate on the Bruce protocol. Participants will be informed of the study, screened, and consented to participate at one time. During testing, participants will be gathered until adequate power is reached.

23.2 The physical therapy class the participants will be drawn from has 37 students total. All willing participants will be screened and consented for inclusion, and data will be gathered until adequate power is reached.

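### Section 11.2 labels an effect size of 0.5 moderate, but nine participants fits 0.5 as Cohen's f, which over the four FSD tests is a largest mean difference of 1.00 to 1.41 SD

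*Protocol*

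**What the plan says.** Protocol section 11.2 reports that "no within-subjects effects sizes were available for an a priori power-analysis for required sample size". It cites 1.26, taken from earlier work comparing groups that scored differently on the FSD test, calls it large, and sets 0.5 for this study: "given their large effect size the investigators felt justified in setting a moderate effect size for the power analysis". The calculation is described as a repeated-measures, within-factors ANOVA with alpha .05, power .80 and a two-tailed hypothesis. The result: "This power analysis determined the need for nine participants". With 37 students in the class, the section concludes that "we have more potential participants than needed to ensure the required power to observe a statistical result if it exists". The scale of 0.5 is not named.

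The figure is then relied on elsewhere. Section 20.2 says: "With nine participants needed per the power analysis, there should be no difficulty recruiting the necessary number of participants". Section 23.1 says: "During testing, participants will be gathered until adequate power is reached". Section 23.2 says: "All willing participants will be screened and consented for inclusion, and data will be gathered until adequate power is reached". No other number in the protocol defines adequate power.

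The design has four FSD tests per participant: one before the Bruce protocol and three after it, at one, five and ten minutes (section 7.1).

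**The concern.** Going from 1.26 to 0.5 and calling the result moderate reads as a cautious reduction of about 60% on one scale (1 − 0.5/1.26 = 0.60). In a repeated-measures ANOVA power calculation, however, the effect size is commonly Cohen's f, which is not a difference in SD units. If 0.5 was entered as f, nine participants is the answer for a much larger fatigue effect than the text suggests.

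What is at stake is how a null result would be read. If testing stopped near nine because adequate power was thought to have been reached, an absence of change in FSD score could be taken as evidence against a moderate effect. The calculation would have addressed only a large one.

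**Working it through.** **Inputs from the protocol.** Effect size 0.5, alpha .05, power .80, N = 9 (11.2); m = 4 tests (7.1, 9.3); class of 37 (11.2, 20.2).

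**Assumptions, not in the protocol.** A common correlation rho between tests, equal SDs, and sphericity (epsilon = 1) unless stated. SD means the between-participant SD of the FSD score at one test.

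**Formula.** Noncentral F with λ = N·m·f²/(1 − rho), df1 = m − 1, df2 = (N − 1)(m − 1). Here f is the SD of the m test means (divisor m) divided by the SD above.

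**Step 1: reproduce nine, with 0.5 as Cohen's f.**
- m = 4, rho = 0.3: λ = 9 × 4 × 0.25/0.7 = 12.86 on 3 and 24 df, power 80.0%. Nine is the exact answer for rho 0.30 to 0.39.
- m = 3, rho = 0.5: power 85.6% at nine and 79.9% at eight, so nine is again exact.
- m = 4, rho = 0.5: seven suffice, and nine give 92%. With alpha .025, nine is exact (86.0%, against 79.5% at eight).

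**Step 2: f = 0.5 in SD units over four tests.** For test means differing by at most D:
- Two low, two high (0, 0, D, D): f = D/2, so D = 1.00 SD.
- Pre-test against three equal post-tests (0, D, D, D): f = 0.433D, so D = 1.15 SD.
- Two middle means (0, D/2, D/2, D): f = 0.354D, so D = 1.41 SD.

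With three tests the smallest value is 0.5/0.471 = 1.06 SD.

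**Step 3: the step down from 1.26.** If 1.26 is a standardised difference between two equal groups, its f is 1.26/2 = 0.63. The reduction on the f scale is 1 − 0.50/0.63 = 21%.

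**Step 4 (secondary): 0.5 on the same scale as 1.26.** A largest difference of 0.5 SD gives f of at most 0.5/2 = 0.25. Power at nine completers, m = 4:

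| Assumed rho | epsilon 1 | epsilon 0.75 |
|---|---|---|
| 0.3 | 25% | 22% |
| 0.5 | 34% | 29% |
| 0.7 | 55% | 46% |
| 0.8 | 74% | 64% |

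Power reaches 80% at rho 0.825 (0.86 with epsilon 0.75). That is the most favourable pattern of means. Pre-test against three equal post-tests needs 0.869, and the least favourable pattern needs 0.912.

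**Step 5: other scales.** If 0.5 is the mean change divided by the SD of the changes, rho drops out and a paired t-test at nine has about 26% power. If 0.5 is partial eta-squared, nine also appears (three measurements with epsilon 0.75 or with alpha .025). At N = 9 and m = 3 that equals f = √(16(1 − rho)/27) = 0.64, 0.54 and 0.42 at rho 0.3, 0.5 and 0.7, or largest differences of at least 1.37, 1.15 and 0.89 SD (f/0.471). Neither reading makes nine enough for a 0.5 SD difference at ordinary correlations.

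**Step 6: what nine completers can detect with 80% power (m = 4).** f = 0.50, 0.42 and 0.33 at rho 0.3, 0.5 and 0.7, which are largest differences of at least 1.00, 0.84 and 0.65 SD (2f, before rounding f). If all 37 students completed, power for f = 0.25 would be 86% at rho 0.3 and 96% at rho 0.5.

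**The case against.** The strongest reply is that nothing stated is numerically wrong. Alpha, power, test, effect size and N agree with one another if 0.5 is Cohen's f, which is the most likely reading given the ANOVA described. On that reading the 80% claim is right for the effect entered, and the dispute is over one adjective. The protocol gives no FSD standard deviation and no smallest important change against which to call 1 SD too large. It also never says that 1.26 and 0.5 share a scale, and its first reason for choosing 0.5 is that the designs differ. All of that stands, and it is why Step 4 is secondary. What it does not answer is that 0.5 is justified only by reference to 1.26, so a reader is left to take it as a difference of half an SD.

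Four stronger readings are tempting, and the protocol does not support them:
- *Nine is an arithmetic error.* It is not. Step 1 reproduces it by several routes.
- *The study has only 25% to 74% power.* Those figures apply only if 0.5 is a standardised difference, and only at the assumed correlations. Section 7.1 says "Each participant will perform the pre-and post-testing in the same day", with post-tests minutes apart, so a rho of 0.83 or more cannot be excluded.
- *The study will enrol only nine.* Nine is a minimum. Section 23.2 invites all willing students, and neither 23.1 nor 23.2 names nine. The link to nine is an inference from its being the only figure given.
- *Leaving out rho and epsilon is itself the fault.* Such inputs may sit in an analysis plan that is not shown. The point concerns a power claim that the protocol makes itself.

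**Conclusion.** The point holds as a mislabelled effect size behind a power claim. If 0.5 is Cohen's f, as is likely, the stated 80% power at nine is for a largest difference of 1.00 to 1.41 SD across the four tests, not for 0.5 SD. If 0.5 is a standardised difference, nine completers support the claim only from rho of about 0.83 upward, under sphericity and the most favourable pattern of means. The scale of 0.5 is an inference, and every rho and epsilon value here is an assumption.

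The severity is minor to should-fix. The consequence is conditional on collection stopping near nine, and the class is large enough to avoid it. It is still worth correcting, because nine is the only figure that gives the stopping point in 23.1 and 23.2 a meaning.

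**What to change.** In 11.2, state that 0.5 is Cohen's f (if it is), with the number of tests and the rho and epsilon used, and drop the word moderate. Restate the claim as: nine completers give 80% power for f of about 0.50, 0.42 or 0.33 at assumed rho 0.3, 0.5 or 0.7, which are largest differences of at least 1.00, 0.84 or 0.65 SD over four tests.

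Carry the restated claim into 20.2. In 23.1 and 23.2, replace adequate power with a stated number of completers, since sections 3.2 and 13 remove those who miss the heart-rate threshold or the final FSD test.

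The cost is a rerun of the power calculation and rewording in three sections. The stated claim becomes less favourable, but no extra participants are required. If the investigators prefer to keep a moderate effect in the sense of 0.5 SD, the target has to rise: f = 0.25 needs 32, 24 or 15 completers at assumed rho 0.3, 0.5 or 0.7 under the most favourable pattern of means, all within the class of 37.
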